#### 2.3.2 Known Potential Benefits

Participants in this study may have no personal, direct benefits from participation. Although they are not currently identified as a person at risk for contracting anthrax, participants may develop immune responses to the anthrax vaccines being studied in this protocol that are protective against anthrax or that may mitigate anthrax disease following exposure. Even without any personal direct benefits, participants may contribute to a societal benefit through the

improvement of our understanding of these vaccines and by contributing to the protection of persons at risk for or exposed to anthrax.

# 3 STUDY OBJECTIVES AND OUTCOME MEASURES

Refer to Table 1: Study Objectives and Outcome Measures

### 4 STUDY DESIGN

The study is a phase I randomized, parallel-group, double-blind controlled interventional trial in which the safety, tolerability, and immunogenicity of 2 formulations of adjuvanted anthrax vaccine (AV7909), lyophilized and liquid, both manufactured by Emergent BioSolutions, will be assessed and compared. AV7909 is an investigational vaccine that combines the currently licensed Anthrax Vaccine Adsorbed (AVA, BioThrax) with the adjuvant CPG 7909, an oligonucleotide. Forty healthy young adults, 18 to 45 years old, inclusive, who meet all eligibility criteria, will be randomly allocated to one of two study groups in a 1:1 ratio: 20 will receive AV7909 as the thermostable lyophilized product and 20 will receive AV7909 as the liquid product. Stratification by age category and by gender will assure that near equal numbers of younger (18-30 years) and older (31-45 years) males and females will be assigned to each vaccine. The vaccines will be given intramuscularly in a 2-dose schedule, 2 weeks apart. Data entry will be "direct", that is, without the significant use of paper source documents. Participants will be followed for safety and tolerability by in-person visits, electronic reactogenicity records (eMemory Aids), and safety laboratory values. A Safety Monitoring Committee will evaluate the safety data whenever necessary (as determined by the sponsor or principal investigator) and in the event of a halting rule occurring. Immunogenicity will be evaluated by pre-vaccination and multiple post-vaccination assessments of toxin-neutralizing antibodies as determined by ED50 and NF50 and by IgG antibodies against PA measured by ELISA. Participants will be followed for 1 year following the second dose (through approximately Day 380).

Safety will be assessed by evaluation of non-serious unsolicited Adverse Events, Serious Adverse Events (SAEs), Medically Attended Adverse Events (MAAEs), Adverse Events of Special Interest (AESIs) [the AESIs collected in this study are Potentially Immune-Mediated Medical Conditions (PIMMCs)], and by laboratory evaluations. SAEs, MAAEs, and AESIs will be collected from the time of study vaccination through approximately Day 380. Non-serious unsolicited AEs will be collected from Day 1 to Day 64, inclusive. Clinical laboratory evaluations for eligibility will be the following: specific hematology parameters, chemistry parameters, , specific urine tests for drugs of abuse, and hemoglobin A1C. Also, an electrocardiogram will be performed at screening and reviewed by an investigator and cardiologist. The cardiologist will determine if any findings on the electrocardiogram are significant and thereby exclusionary. At approximately Day 29, laboratory tests for hematology and chemistries will be repeated.

Reactogenicity will be measured by the occurrence of solicited injection site and systemic reactions in the week after each study vaccination (Days 1 through 8 and target of Days 15 through 22, inclusive). The window for dose 2 includes Days 15 to 18. For participants who are vaccinated beyond Day 15, the study schedule will adjust so that a full week of reactogenicity data are collected, regardless. Any of these events that persist on Day 8 or Day 22 (or the final

day of the second reactogenicity period) will be followed until resolution. Only pharmacy personnel, the Emmes unblinded team, and an unblinded vaccinator and checker will have access to the study codes; all other study personnel and all participants will be blinded.

Immunogenicity testing will include performing serological assays to assess for toxin neutralizing antibodies (reported as ED50 and NF50), the gold standard assay for assessing response and protection following anthrax vaccines, prior to vaccination and on approximately Days 8, 15, 22, 29, 64, 195, and 380. Should the second dose of vaccine be given after Day 15 (the acceptable window is Days 15 to 18, inclusive) the remainder of the study schedule days shift accordingly, to maintain the intervals in the schedule. In addition, anti-PA IgG antibodies will be measured by ELISA from the serum of participants, on those same days.

For additional details on study procedures and evaluations and the study schedule by study visits/days, see Sections 7 and 8 as well as Appendix A: Schedule of Study Procedures and Evaluations and Appendix B: Adverse Events of Special Interest.

### 5 STUDY ENROLLMENT AND WITHDRAWAL

Forty (40) males and non-pregnant females, 18 to 45 years of age, inclusive, who are in good health and meet all eligibility criteria will be enrolled at one VTEU site. The target population will reflect the community at large at the participating VTEU site, but in order to assure enrollment of near equal numbers in each study group (AV7909 Liquid and AV7909 Lyophilized) by sex and age category, a stratified enrollment procedure will be employed. The strata used will be males/females and age 18-30 years/age 31-45 years.

The estimated time to complete enrollment in this trial, from first participant enrolled until last participant enrolled, is approximately 3 months. Information regarding this trial may be provided to potential participants who have previously participated in vaccine trials, other than anthrax vaccine trials, conducted at the VTEU site. Other forms and/or mechanisms of recruitment may also be used. The IRB will approve the recruitment process and all materials prior to use.

Participant inclusion and exclusion criteria will be assessed by a study clinician licensed to make medical diagnoses and listed on the Form FDA 1572 as the site principal investigator (PI) or sub-investigator.

No exemptions are granted on participant inclusion or exclusion criteria in DMID-sponsored studies. Questions about eligibility will be directed toward the DMID Medical Officer for this trial.

# 5.1 Eligibility Criteria

# 5.1.1 Participant Inclusion Criteria

Participants eligible to participate in this trial must meet all the following inclusion criteria:

- 1. Provide written informed consent prior to initiation of any study procedures.
- 2. Understand and comply with planned study procedures, including completion of the electronic memory aid, and be available for all study visits.
- 3. Agree to the collection of venous blood, per protocol.
- 4. Have adequate venous access for phlebotomies.
- 5. Be a male or non-pregnant female, 18 to 45 years of age, inclusive, at the time of enrollment.

## 6. Be in good health.

As determined by medical history and physical examination to evaluate acute or currently ongoing chronic medical diagnoses or conditions, which would affect the assessment of the safety of participants or the immunogenicity of study vaccinations. Chronic medical diagnoses or conditions, defined as those that have been present for at least 90 days, should be stable (not worsening) for the last 60 days (no hospitalizations, emergency room or urgent care for condition, or invasive medical procedure and no adverse symptoms that need medical intervention such as medication change indicative of worsening/supplemental oxygen). This includes no change in chronic prescription medication, dose or frequency, indicative of worsening disease, in the 60 days prior to enrollment. Any prescription change that is due to change of health care provider, insurance company, etc., or that is done for financial reasons, will not be considered a deviation of this inclusion criterion. Participants may be on chronic or as needed (prn) medications if, in the opinion of the site PI or appropriate sub-investigator, they pose no additional risk to participant safety or assessment of reactogenicity and immunogenicity and do not indicate a worsening or treatment of continued symptoms of medical diagnosis or condition. Herbals, vitamins, and supplements are permitted.

- 7. Have an oral temperature less than 100.0°F.
- 8. Have a pulse 51 to 100 beats per minute, inclusive.
- 9. Have a systolic blood pressure 85 to 140 mmHg, inclusive.
- 10. Have a diastolic blood pressure 55 to 90 mmHg, inclusive.
- 11. Have a calculated body mass index (BMI) less than or equal to 35.0 kg/m^2 at screening.
- 12. Screening laboratories in table below are within acceptable parameters.

2

Test	Eligibility Criterion
BUN	<23 mg/dL
Serum creatinine (female)	<1.3 mg/dL
Serum creatinine (male)	< 1.4 mg/dL
Alkaline phosphatase (female)	<147 U/L
Alkaline phosphatase (male)	<192 U/L
ALT (aka SGPT)	<68 U/L
Total bilirubin	< 1.3 mg/dL
Hemoglobin (female)	>10.9 g/dL
Hemoglobin (male)	> 12.4 g/dL
White blood cell count	3000-12,000 cells/mm 
Absolute eosinophil count	<1201 cells/mm 
Absolute neutrophil count	>1200 cells/mm 
Platelets	>126,000 cells/mm 
Hemoglobin A 1 C	<6.5%

Urine for Drugs of Abuse*	All negative
HBsAg	Non-reactive
HCV antibodies	Negative
HIV 4 th generation test	Negative

\*amphetamines, barbiturates, benzodiazepines, cocaine, methadone, opiates, oxycodone/oxymorphone, phencyclidine (PCP), and propoxyphene. Note that a prospective participant with a positive urine for drugs of abuse test for a medication reported by the participant and used to treat a condition that does not make them otherwise ineligible, may be permitted to enroll, at the discretion of the investigator or his designee.

13. Have no clinically significant findings on 12-lead electrocardiogram.

Clinical significance will be determined by a cardiologist. Examples of findings that will lead to exclusion are significant left ventricular hypertrophy, right or left bundle branch block, advanced A-V heart block, non-sinus rhythm (excluding isolated premature atrial contractions), pathologic Q wave abnormalities, significant ST-T wave changes, prolonged QTc interval.

14. Heterosexually active females of childbearing potential must use an acceptable contraception method from at least 30 days before the first until 60 days after the second study vaccination.

Not sterilized via bilateral oophorectomy, salpingectomy, hysterectomy, or successful Essure® placement (permanent, non-surgical, non-hormonal sterilization) with documented radiological confirmation test at least 90 days after the procedure, and still menstruating or <1 year has passed since the last menses, if menopausal.

Includes full abstinence from sexual intercourse with a male partner, monogamous relationship with vasectomized partner who has been vasectomized for 180 days or more or shown to be azoospermic prior to the participant receiving the study vaccination, barrier methods such as condoms or diaphragms/cervical cap, intrauterine devices, NuvaRing®, tubal ligation, and licensed hormonal methods such as implants, injectables or oral contraceptives ("the pill").

- 15. Females of childbearing potential must have a negative serum pregnancy test at screening and a negative urine pregnancy test within 24 hours prior to each study vaccination.
- 16. For a female with potential to become pregnant, she understands that in the event of pregnancy during the study she will be asked to allow us to follow her during pregnancy through outcome.
- 17. Must agree to have blood collected, stored, and potentially used for auto-antibody studies (if a suspected PIMMC occurs in this participant).

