## 8.2.2 Visit 3, Day 15, Clinic Visit (Second Vaccination) (Window: Day 15 to 18, inclusive)

- Interim medical history, including an assessment for new medical conditions, stability of chronic diseases and symptoms suggestive of AESIs (PIMMCs), will be obtained by interview of participants and any changes since the previous clinic visit will be noted.
- All changes to concomitant medications will be recorded on the appropriate eCRF.
- All MAAEs and AE/SAEs will be recorded on the appropriate eCRF.
- A targeted physical examination, including an assessment for signs suggestive of AESIs (PIMMCs), may be performed, if indicated based on review of interim medical history, by a study clinician licensed to make medical diagnoses and listed on the Form FDA 1572 as the site PI or sub-investigator.
- Venous blood will be collected for serological assays (TNA and anti-PA ELISA).
- Criteria for receipt of the second vaccination will be reviewed with participants prior to
  the second study vaccination to ensure continued eligibility. These criteria are identical to
  the eligibility criteria, with the following exceptions: continued consent must be
  confirmed, age will not be re-confirmed, physical exam will not be required to determine
  good health, BMI will not be recalculated, screening labs will not be repeated, and
  screening electrocardiogram will not be repeated.
- Vital signs (oral temperature, pulse, and BP) will be obtained prior to study vaccination to ensure continued eligibility. Vital signs assessed on Day 1 prior to study vaccination will be considered as baseline. Participants must not eat or drink anything hot or cold, or smoke within 10 minutes prior to taking oral temperature.
- A urine pregnancy test will be performed locally by the site within 24 hours prior to study vaccination for all females of childbearing potential. Results must be negative and known prior to study vaccination. Women of childbearing potential will be counseled to avoid pregnancy until 60 days after the second (final) vaccination, i.e., Day 75.
- Pre-administration reactogenicity assessments will be performed immediately prior to study vaccination to establish baseline.
- Participants will then receive their second dose of study vaccine via a single IM injection into the deltoid muscle of the opposite arm of the first vaccination. The site of injection (right or left arm) and time of study vaccine administration will be recorded on the

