## 14.4 Exclusion of Women, Minorities and Children (Special Populations)

This trial will be inclusive of all interested persons, 18 to 45 years of age, who meet the Participant Inclusion Criteria (see Section 5.1.1) and do not meet the Participant Exclusion Criteria (see Section 5.1.2), regardless of religion, sex or ethnic background. Should the outcome of this trial be deemed acceptable, additional trials may be initiated including those in other populations.

It is unknown if AV7909 poses any risks to an unborn child. Females of childbearing potential must utilize a highly effective method of contraception that is defined as one that results in a low failure rate (i.e., less than 1% per year) when used consistently and correctly (effective methods of birth control are outlined in the inclusion criteria, section 5.1.1). In addition to contraceptive use, all females of childbearing potential will be required to have a negative pregnancy test within 24 hours prior to each study vaccination. Female participants who become pregnant while participating in this trial will be asked to consider allowing the study team to follow them during pregnancy and record the outcome.

Children will not be included in this trial.

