Appendix B: Adverse Events of Special Interest

## APPENDIX A. SCHEDULE OF STUDY PROCEDURES AND EVALUATIONS

Study Visit (V)	0	1	2	3	4	5	6	7	8	Early Termination
Study Day#	pre	1	8	15#	22#	29#	64#	195#	380#	
Window Open	-28	1	8	15	22	27	60	188	373	
Window Close	-2	1	11	18	25	31	68	202	387	
Study Week	pre	1	1	2	3	4	9	28	54	
Activity/Procedure										
Inform prospective participant about study details 	X									
Obtain informed consent, HIPAA authorization, enroll 	X									
Obtain, record, update demographics, medical history, concomitant medications 	X	X	X	X	X	X	X	X	X	X
Perform physical examination 	X	X	X	X	X	X	X	X	X	X
Collect blood/urine for eligibility or post- vaccination safety 	X					X				X
Perform pregnancy test 	X	X		X						
Perform 12-lead electrocardiogram 	X									
Review eligibility criteria or criteria for subsequent vacination 	X	X		X						
Perform randomization 		X								
Vaccinate 		X		X						
Perform post-vaccination reactogenicity assessment, instruct on eMemory Aid, & provide study related materials 		X		X						
Counsel on avoidance of pregnancy 	X	X	X	X	X	X	X			
Review memory aid (solicited AEs/reactogenicity) & confirm data 			X		X					
Examine study vaccination site 			X		X					X
Collect blood – Toxin Neutralization Assay (TNA) and anti-PA IgG by ELISA 		X	X	X	X	X	X	X	X	X
Collect blood – to be stored for use if PIMMC occurs 	X									
Perform assessment  of non-serious unsolicited AEs		X	X	X	X	X	X			X
Perform SAE, MAAE, and AESI assessment 		X	X	X	X	X	X	X	X	X

\* Note that all visits after Visit 3 (target Day 15, second vaccination) are based on the day that Visit 3 occurs. If it occurs on Day 15, all subsequent visits and windows are as written in Appendix A. If it occurs after Day 15, subsequent visit days will be adjusted to maintain the intervals. For example, if Visit 3 occurs on Day 16, then the remaining target Days are 23, 30, 65, 196, and 381. The number of days in the accompanying acceptable windows for each visit will remain the same. The Days for each visit, as written in the Table above and described throughout the protocol and elsewhere, reflect the schedule assuming that Visit 3 occurs on Day 15.

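### Protocol Section 14.4 states a contraception standard of under 1% failure per year, but inclusion criterion 14, the rule the site reviews, carries no failure limit

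*Protocol*

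**What the plan says.** Section 14.4 sets the stricter text: "Females of childbearing potential must utilize a highly effective method of contraception that is defined as one that results in a low failure rate". The sentence then gives the number, the condition of use and a cross-reference: "failure rate (i.e., less than 1% per year) when used consistently and correctly (effective methods of birth control are outlined in the inclusion criteria". It has no method list of its own.

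Section 5.1.1, criterion 14, says that heterosexually active females of childbearing potential "must use an acceptable contraception method", from 30 days before the first vaccination to 60 days after the second. Footnote 5 lists what counts, including "barrier methods such as condoms or diaphragms/cervical cap, intrauterine devices". It gives no failure rate and asks for no second method.

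Section 2.3.1 speaks of effective contraception over the same period, in a narrative of risks.

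On how the criteria are applied, Section 5.1.1 opens: "Participants eligible to participate in this trial must meet all the following inclusion criteria". Section 5 adds: "No exemptions are granted on participant inclusion or exclusion criteria in DMID-sponsored studies". Section 8.2.2 repeats the review before "the second study vaccination to ensure continued eligibility. These criteria are identical to" the eligibility criteria apart from a list of exceptions. The Appendix A row "Review eligibility criteria or criteria for subsequent vacination" is marked at Visits 0, 1 and 3.

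**The concern.** Section 14.4 is where an IRB looks for the protection offered to women who could become pregnant. It offers a numeric one. The eligibility rule that would have to deliver that protection does not contain the number.

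The subject is not trivial for this product. Section 2.3.1 reports that AV7909 has had no reproductive toxicity studies, that BioThrax can harm a fetus, and that CPG 7909 was embryolethal or teratogenic in animals, though at doses far above the vaccine dose. Appendix A schedules no pregnancy test after Visit 3, while contraception is required to Day 75. After dose 2, prevention therefore rests on contraception and counselling. That is the period in which the contraception standard matters most.

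**Working it through.** No sample size, power or event figure enters, so the check is a comparison of texts.

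**Step 1. The two rules side by side.**

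- Strength: Section 14.4 says highly effective; criterion 14 says acceptable.
- Failure limit: Section 14.4 gives under 1% per year with consistent, correct use; criterion 14 and footnote 5 give none.
- Population: Section 14.4 covers females of childbearing potential; criterion 14 covers those who are heterosexually active.
- Methods: Section 14.4 defers to Section 5.1.1. Footnote 5 there names 7 groups: abstinence, a vasectomized partner, barrier methods, intrauterine devices, the vaginal ring, tubal ligation and licensed hormonal methods. None of the 7 carries a failure limit. Each is enough alone, barrier methods included.

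**Step 2. Which rule is reviewed.** The eligibility criteria are reviewed at screening (Section 8.1.1), at Day 1 (Section 8.1.2) and before dose 2 (Section 8.2.2). Before dose 2 there are 6 exceptions: consent is reconfirmed rather than taken anew, and age, physical examination, BMI, screening laboratory tests and electrocardiogram are not repeated or required. Contraception is not among them, so criterion 14 applies at all 3 reviews. The under-1% limit is part of the criteria at 0 of the 3. These counts restate one omission and are not separate defects.

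**Step 3. What the omission means in practice.** Take a participant whose only method is a condom or diaphragm. She meets criterion 14. Whether she meets Section 14.4 depends on the annual failure rate of that method under correct use, call it *f*, which neither document gives.

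- If *f* is under 1%, she meets both texts, and only the wording needs aligning.
- If *f* is 1% or more, she meets Section 5.1.1 but not Section 14.4.

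The same question arises for every other listed method, since the documents give no rate for any of them.

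**Step 4. What else protects the participant.** For women of childbearing potential there is a serum pregnancy test at screening and a urine test within 24 hours before each dose. Dose 2 is withheld if pregnancy occurs. Counselling to avoid pregnancy is scheduled at 7 visits, Visit 0 to Visit 6 (Day 64). With dose 2 on Day 15, contraception runs to Day 15 + 60 = Day 75. The last scheduled pregnancy test is at dose 2.

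**The case against.** The strongest reply is that Section 14.4 itself points to Section 5.1.1. Read together, Section 14.4 gives the aim and footnote 5 lists the methods that the sponsor accepts as meeting it, so there is no conflict. That reading is possible, but it does not remove the problem. It attaches a numeric claim to every method in a list that never mentions the number, and the documents offer no support for the claim. On the other reading, the limit is real and the eligibility rule does not apply it. Either way one text needs correcting.

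It can also be said that Section 14.4 binds the site as much as criterion 14 does, because Section 15.6 treats any noncompliance with the protocol as a deviation. That is right. But no scheduled review asks about the limit, and a site that follows criterion 14 has no prompt to apply it.

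Three further objections stand and limit the point:

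- A reader might infer that barrier methods breach the 1% limit and should be singled out. The documents give no failure rates, so this cannot be concluded from them.
- A reader might propose that a barrier method count only alongside a listed non-barrier method. That is redundant, because the non-barrier method already satisfies criterion 14 alone.
- A reader might count three rival standards by adding Section 2.3.1. That section is narrative, its period agrees with criterion 14, and its word *effective* is the one Section 14.4 uses when it refers to the Section 5.1.1 methods. The mismatch is between two texts.

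**Conclusion.** The point holds as a minor inconsistency in participant protection. Section 14.4 states a limit that criterion 14 and footnote 5, reviewed at screening, Day 1 and before dose 2, do not contain. The two texts also differ on whether the requirement covers all females of childbearing potential or only those who are heterosexually active.

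This conclusion rests on the wording alone and needs no assumption about any method. Whether a participant could in fact meet one text and fail the other does need an assumption, namely that some listed method fails in 1% or more of correct users per year. That is left open, and no number of pregnancies is estimated. Nothing in the endpoints, sample size or analyses is touched.

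**What to change.** Adopt one standard, by either route:

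- **(a) Enforce the limit.** Write the under-1% limit, with its consistent-and-correct-use condition, into criterion 14, and have the sponsor keep in footnote 5 only methods that it can show meet the limit. The cost is slightly narrower eligibility, and it affects future enrolment only.
- **(b) Restate the claim.** Reword Section 14.4 to require an acceptable method as listed in inclusion criterion 14, and delete the under-1% claim. Nobody is excluded and no participant's risk changes, but the stated standard becomes less favourable. This route is still useful if enrolment has closed, because Section 16 says the protocol will be posted publicly.

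With either route, use the same population wording in both sections, and use the chosen term in Section 2.3.1 for tidiness. The change is a few sentences in a protocol amendment. The SAP needs no change.
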